## **Introduction**

Late and long term sequelae following breast cancer treatment, such as lymphedema, affects patients quality of life due to many factors, amongst these are reduced functional ability due to affected shoulder and arm function, emotional problems and negative view on body image following treatment. (1,2)

A growing body of literature shows promising results for reconstructive surgery as a physiological treatment of secondary lymphedema, resulting in a decreased rate of sequelae following breast cancer treatment, such as reduced volume of the affected extremity and episodes of erysipelas, improved quality of life and functionality of the limb. (3–7) However, there is a lack of systematics when it comes to patient characteristics and surgical procedure, which necessitates further studies to address this challenge. Recent research emphasizes the importance of correctly identifying which vessels to anastomose, in order to select the most suitable vessels and patients for treatment; to carefully plan and personalise the treatment plan, based on the patient's physiology. (2,6,8–11)

The primary aim of this study is to investigate and test if we can correctly identify lymphatic vessels and venules in close proximity to each other using combined ICG lymphography and ultra high frequency ultrasonography for identification prior to LVA surgery.

## **Background**

Breast-cancer related lymphedema is a life-disabling side-effect of breast cancer treatment, affecting more than 1 in every 5 patients. (12,13) With breast-cancer being the most common cancer diagnosis in women, affecting up to 2.3 million new cases globally, and with a generally high survival rate of 80% or higher in developed countries, the number of breast-cancer survivors with long-term sequela is significant. (14,15) In 2020, 5083 patients were diagnosed with breast cancer in Denmark, which based on the incidence, gives an estimated number of 800 or more of these patients will develop lymphedema per year. (16)

Due to a disruption to the lymphatic system with inadequate drainage, protein-rich lymph fluid is accumulated in the interstitial tissue, causing excessive swelling of the upper extremity, breast, and truncus of the treated side. (17) This accumulation of fluid promotes chronic inflammation in

the extracellular matrix and fibrosis and hypertrophy of the adipose tissue, followed by annihilation of the lymphatic vessel lumen due to sclerosis. (8)

Compression garments and physiotherapy have been considered the standard treatment and rehabilitation for lymphedema. (18) Some of the disadvantages with these treatments include variability in patient compliance, clinical effect and lack of statistical significant results. (19)

As breast cancer is the most common cancer among women, with an increasing survival rate due to improved treatment, the rehabilitation and treatment options for long-term sequela are in high demand, affecting patients physical and mental health. (2–6,20–22)

These long-term sequelae include swelling, arm heaviness, tightness, pain, weakness and affected functionality of the arm. Moreover, breast-cancer survivors with breast cancer related lymphedema report emotional sequelae, including deterioration of generic mental health, social role functioning, life and social activities and bodily pain. (1,20,22) In addition to this, the condition generally worsens over time, emphasizing the need for long-term treatment of lymphedema.(18,23)

Physical interruption of flow, radiation, and obesity has been proposed as major causes of breast cancer related lymphedema because of lymphatic vessel ectasia and dysfunctional valves. The volume of interstitial fluid exceeds the rate of lymphatic flow, resulting in a state of increased interstitial fluid; what we know as lymphedema. This stasis of fluid cause a chronic inflammation with deposition of fibro-adipose tissue, which in turn further decreases the lymphatic function. (8,23) Lymphovenous anastomosis surgery is an attempt to re-establish the lymphatic flow, utilizing the patient's own lymphatic- and venous vessels.(17) Other treatment modalities that have been proposed as treatment options for lymphedema includes lymph node transplantation, liposuction and de-bulking procedures, stem-cell therapy and medical therapy. (8,24)

Prior to this study, we reviewed the literature of the field; a literature search was conducted focusing on lymphovenous anastomoses. Several studies and reviews emphasize the importance of preoperative planning based on disease pathophysiology. Surgical treatment seems effective in selective patient groups, but systematic studies for this are lacking. (2,10,11,25–27) It is based on this lack of knowledge of patient characteristics and preoperative planning that the project's hypothesis and idea was formed.

ICG lymphography is commonly used for identification of lymphatic vessels, and is considered superior to other modalities such as computed tomography (CT) and lymphoscintigraphy. (27,28) The ICG dye in the lymphatic vessels can be detected by an infrared camera. However, until recently, the identification of adjacent venules remained a challenge. Ultra high frequency ultrasound may have solved the challenge of identifying the small venules prior to surgery. The combined use of ICG lymphography and ultra high frequency ultrasound may be the key to optimise patient selection and preoperative planning of lymphovenous anastomosis surgery. (27,29–31)

We therefore wish, based on the knowledge, to add to the knowledge regarding targeted surgical treatment of lymphedema. Hopefully this pilot study that uses a combination of an ICG camera and ultra high frequency ultrasound will enable us to propose an algorithm, that can be used for lymphedema patient, when selecting between surgery and other treatment modalities. Thus, we hope our method helps to specify which patients may benefit from surgery. The primary aim of this pilot study is to investigate and test if we can correctly identify lymphatic vessels and venules in close proximity to each other using a combination of indocyanine green (ICG) lymphography and ultra high frequency ultrasound prior to lymphovenous anastomosis.

### **Material and methods**

[figure not shown]
ICG lymphography is a technique for visualization of the superficial lymphatic systems. By injecting ICG subcutaneously, it enables a real-time visualization of the lymphatic networks through a minimally invasive procedure. ICG is a non-toxic tracer with low risk of complications; 0.17% risk in general, and 0,02% for nonsevere shock, by intravenous injection. Severe allergic reaction, including anaphylactic shock, affects fewer than 1/10.000 patients. (32,33)

The ICG lymphography is performed and used for visualisation of the superficial lymphatics for preoperative planning, using 0.1 mL ICG (2.5 mg/mL Verdye, Diagnostic Green, Ascheim, Germany). The dye is injected subcutaneously at the wrist, near the ulnar border of the palmaris longus tendon, and in the 1st and 3rd web space of the hand. Scans are performed using an infrared camera, the HyperEye medical system (MNIRC-501, HEMS; Mizuho Co., Tokyo, Japan). During real-time visualization, lymphatic vessels are drawn up on the patients arm using a permanent marker. (32,34)

Ultra high frequency ultrasound (>30MHz) has the ability to visualize small, superficial anatomical layers. (10,30,35) Using this ultra high frequency ultrasound, following the mapped lymphatic vessels, venous vessels are found nearby and likewise mapped for anastomosis. The ultrasound scans are performed using a 70MHz probe (Vevo® MD Imaging System, Fujifilm, VisualSonics Inc.). The number of LVA anastomosis sites is set to a minimum of two sites per extremity. The number of mapped lymphatics vessels and venoles are compared to the number identified during surgery and recorded.

The secondary outcomes includes: 1) changes of arm volume over time, 2) changes of lymphatic flow pattern before and after surgery by ICG lymphangiography, 3) changes in health-related quality of life by the use of the LYMPH-Q questionnaire and 4) changes in L-Dex score and body composition measured with bioimpedance before and 3 months after LVA surgery. (32,36,37,37–39)

#### Volume calculation

*Figure 1: Illustration of circumference tape measurements*

Manual circumferential measurements are taken from both arms for volume calculation, see figure 1, based on the formula for multiple blunt cones:

$$Volume = \frac{1}{3} * \pi * (r_1^2 + r_1 r_2 + r_2^2) * h$$

The formula is based on the measurements illustrated in figure 2.

[figure not shown]

Figure 2: Measurements for volume calculations of a blunt cone

#### Water displacement volume assessment

The water displacement test estimates the volume of the arm, based on lowering the extremity in a basin of water, and calculating the water volume difference in mL.

#### Classification of lymphedema

Video recordings of ICG lymphographies are stored for later classification of the lymphedema. Staging will be done using the MD Anderson scale; a classification system based upon pattern recognition of the dermal backflow from the ICG lymphography, see table 1. (32)

MD Anderson stage	ICG lymphography findings
Stage 0	No dermal backflow
Stage 1	Many patent lymphatics and minimal dermal backflow
Stage 2	Moderate number of patent lymphatics and segmental dermal backflow
Stage 3	Few patent lymphatics with extensive dermal backflow
Stage 4	Dermal backflow involving the hand
Stage 5	ICG does not move proximally to injection site

Table 1: MD Anderson classification based upon ICG lymphography findings.

#### Quality of life

The LYMPH-Q Upper extremity module questionnaire is a validated patient-reported outcome tool for women with breast cancer related lymphedema. The module contains seven individual scales, measuring: symptoms, function, appearance, psychological function, and satisfaction with

information on lymphedema and satisfaction with arm sleeve. Each scale gives an independent score, which can be used for comparison of change over time. (37)

#### Impedance measurements

L-Dex score is a measurement of extracellular fluid of the arm. A stand-on device with electrodes at the hands and feet, estimates the extracellular fluid through electric impulses between these electrodes. It is a non-invasive procedure without any discomfort for the patient. A number between -10 and 10 is considered normal, and diagnostic for lymphedema if above 10. The score correlates with the limb volume and lymphatic function. (38,39)

The same stand-on device also measures body composition through electric impulses, including total body water (TBW) (L), extracellular fluid (ECF) (L), intracellular fluid (ICF) (L), protein and minerals (%), fat mass (FM) (kg), active tissue mass (ATM) (kg) and skeletal muscle mass (SMM) (kg). Following calculations will be compared prior to surgery and 3 months after:

- ECF/TBW (%)
- ICF/TBW (%)
- TBW/weight (%)
- (Proteins and minerals)/weight (%)
- FM/weight (%)
- ATM/weight (%)
- SMM/weight (%)

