- 6) Changes in measurements of body compositions before and 3 months after LVA surgery.

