### **Database**

OPEN REDCap – Research Electronic Data Capture, will be applied for a secure storage of all data. REDCap is a worldwide online system developed for non-commercial clinical research. Data will be stored on OPEN's servers in the Region of Southern Denmark. Here, data is entered via an encrypted connection and meets current data protection requirements. The database will primarily be used to enter and store clinical data, as well as a few simple calculations based on these clinical data, for example BMI calculation. Only members of the research group will have access to this database. No contractual agreement that limits this access, is relevant.

As a starting point, the database will exist until the 31st of January 2024. As the study is a pilot study, there is, however, the possibility of extension with the inclusion of several test subjects for further exploratory study.

Objective measured data, as well as any general personal data that does not already appear in the patient journal, will originally be collected by the primary investigator during the examination.

Collected data and data from the patient's record is then transferred to the REDCap database by the primary investigator. Written informed consent for participating in the project, including collecting information from the patient's examination and journal, is obtained at the patients' first consultation in the outpatient clinic. Only patients who provide written, informed consent is enrolled in the project. No data is collected nor known to the researcher prior to this.

The consent gives the trial supervisor, sponsor and sponsor's representatives as well as any control authority direct access to obtain information in the patient's medical record, as part of the implementation of the research project as well as for control purpose.

The LYMPH-Q questionnaire is completed prior-to and 3 months after the intervention on paper form, which is subsequently entered into the REDCap database by the medical student.

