## **Sample size and Statistics**

No statistical methods are applied in evaluating the sample size and power for this pilot study, as it is a hypothesis generating study. (46) In the case of positive results, this pilot study will form the basis for further clinical study with calculation of a relevant population size.

With the previous experience in the research unit with inclusion of 20 lymphedema patients, it is considered realistic to include 10 patients for this pilot study. In addition, there are already three patients referred to the Department of Plastic Surgery, OUH, who has been evaluated as relevant candidates for LVA surgery.

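### Does dividing protein and minerals, listed in %, by body weight spoil one of the body-composition comparisons?

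*Protocol*

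**What the plan says.** All of the relevant text is in the Protocol, under Impedance measurements. Each output of the stand-on device is given a unit. The fluids are in litres: "total body water (TBW) (L), extracellular fluid (ECF) (L), intracellular fluid (ICF) (L"). The remaining outputs are "protein and minerals (%), fat mass (FM) (kg), active tissue mass (ATM) (kg) and skeletal muscle mass (SMM) (kg"). Protein and minerals are thus the only output listed as a percentage.

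The section continues: "Following calculations will be compared prior to surgery and 3 months after". Seven ratios follow, each labelled per cent. One is "Proteins and minerals)/weight" (the quoted words begin inside an opening bracket). The text does not say what the device percentage is a percentage of, and it gives no mass for protein and minerals.

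Body composition belongs to the fourth secondary outcome in Material and methods: "changes in L-Dex score and body composition measured with bioimpedance before and 3 months after LVA surgery". It returns as item 6 of the comparisons under Collection of Data: "Changes in measurements of body compositions before and 3 months after LVA surgery". Neither place gives a unit, so neither settles the point.

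**The concern.** A quantity already expressed in per cent, divided by a weight in kilograms, has the unit per cent per kilogram. It cannot carry the per cent label that the Protocol gives it. None of the other six ratios starts from a percentage.

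If the entry were carried out as written, this component of a secondary outcome would respond to weight as well as to composition. A patient who lost weight between baseline and 3 months would appear to gain protein and minerals, and one who gained weight would appear to lose them. The Database section says the system will hold "a few simple calculations based on these clinical data, for example BMI calculation", so a formula copied from the Protocol could in principle become a calculated field and be applied to every patient.

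**Working it through.** The Protocol states no figure to reproduce here. The check is one of units, followed by the size of the error under each way of reading the entry.

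**Units of the seven ratios**, using the listed unit of each output and weight in kg:

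- ECF/TBW and ICF/TBW: L/L, a proper percentage.
- FM/weight, ATM/weight and SMM/weight: kg/kg, a proper percentage.
- TBW/weight: L/kg, a percentage once 1 L of water is taken as 1 kg.
- Protein and minerals/weight: %/kg as listed, not a percentage.

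**Three readings of the last entry.** The Protocol gives neither a share nor a body weight, so I assume 20% and 70 kg for illustration. The mass is then 0.20 × 70 = 14 kg.

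1. *The output is a mass in kg and the listed unit is a slip.* The ratio is 14/70 = 20%. After a 5% weight loss at constant composition it is 13.3/66.5 = 20%. False change: 0.
2. *The output is already a percentage of body weight and the entry only names it.* The value is 20% at both visits. False change: 0.
3. *The percentage is divided by weight as written.* The value is 20/70 = 0.286 % per kg. After a 5% loss it is 20/66.5 = 0.301.

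Under reading 3, with a constant percentage and a relative weight change w, the false relative change is 1/(1 + w) − 1. It depends on neither the assumed share nor the starting weight:

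- w = −5%: 1/0.95 − 1 = +5.3%
- w = −3%: 1/0.97 − 1 = +3.1%
- w = +3%: 1/1.03 − 1 = −2.9%
- w = +5%: 1/1.05 − 1 = −4.8%

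These weight changes are also assumptions; the Protocol states no expected change.

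**Which reading the text supports.** Readings 1 and 2 both give a result in per cent, as the label requires. Reading 3 does not. The entry also stands beside three others of the same form (fat, active tissue and skeletal muscle mass over weight), each of which is a share of body weight. The natural sense of the fourth is therefore protein and minerals as a share of body weight.

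**Would reading 3 go unnoticed?** It lowers the value by a factor equal to the body weight in kg: 20/0.286 = 70 under the assumed figures. A value near 0.3 in a column expected to hold values near 20 would stand out at data entry or in the first summary table.

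**The case for a change.** The strongest case for a correction is that the two entries do conflict and nothing else in the Protocol reconciles them. The units stand in running text with clean neighbours, so a fault in text extraction is not a likely explanation. The Protocol calls the listed items calculations, and the other six are true divisions, which favours a division here too. The outcome is a named one, and the correction would cost a look at one device printout and one line of text.

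The textual point stands in full. The rest carries less weight. If a division is meant, the per cent label implies that the input is a mass, which is reading 1 and harmless. The database argument is an inference: the Protocol's only example of a calculated field is BMI, and it does not say that any body-composition ratio will be computed there. A low cost is not a gain when the likely readings give the same result.

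One residual doubt deserves mention. The device percentage could have a base other than body weight. Reporting it directly would then not give a share of body weight, and it would have to be turned into a mass before division. The Protocol's own label already says what the analyst should end up with, and the printout will show the base, so this is a routine step in preparing the data.

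**Conclusion.** No change to the plan is called for. The listed unit and the ratio do not fit if taken literally, but this is a clerical slip whose intended meaning, protein and minerals as a percentage of body weight, can be recovered from the label and the neighbouring entries. Under either reading that respects the label, the effect on the comparison is zero. That holds provided the device output is a mass or a percentage of body weight, or is first converted to a mass if its base is something else.

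The literal reading would produce a false change of roughly 3% to 5% for weight changes of 3% to 5%, but it contradicts the Protocol's own label and puts the value off scale by a factor equal to the body weight in kg. The reach is small in any case: one of seven ratios, within one secondary outcome, in a pilot of 10 patients for which "No statistical methods are applied in evaluating the sample size and power for this pilot study". The primary outcome, a count of mapped vessels against those found at surgery, and the other six ratios do not depend on it.

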#### **Design and population**

This study is designed as a hypothesis generating pilot study with a planned inclusion of 10 patients with a 3 months follow-up period. The research unit has previously conducted studies on the same patient group with the inclusion of 20 patients over a similar project duration. It is therefore considered realistic with the inclusion of 10 patients for the current pilot study for the given period of time.

The inclusion of patients, the surgical procedure and follow-up evaluation will take place at the Department of Plastic Surgery Odense University Hospital (OUH), Denmark, over a period reaching from the 1st of February 2022 till the 31st of January 2024.

The study population is based upon patients who is referred to the outpatient clinic at the Department of Plastic Surgery OUH for assessment of their upper-extremity lymphedema. Only patients who is clinically evaluated to be a candidate for the lymphovenous anastomosis, will be informed and invited to participate in this trial. Information about the surgical procedure is given by a specialist in plastic surgery at the outpatient clinic. Information about the study will be given to the patient in the outpatient clinic no later than 14 days before scheduled surgery, under normal private conditions by the primary investigator.

Patients will receive both oral and written information regarding the project, and are given a reflection time following the legislation over a period of 14 days, with the possibility of withdrawal at any time. The patient is also informed orally and in written form about the possibility of an attendant, which is recommended to the patient.

Only patients who provide written, informed consent will be enrolled in the project.

Included patients will be seen for baseline measurements prior to surgery, and for follow-up evaluation 3 months after the intervention. In addition, the patient will be seen in the department, 14 days and 3 months after surgery, for suture removal and examination, as part of the department's treatment follow-up.

If patient decline to participate in the study, they will still receive the surgery, follow their own course of treatment in the department, separate of this study.

Patients with breast cancer related pitting-lymphedema in one of their upper extremities, who is above the age of 18 and capable of providing informed consent, is included. If pitting edema does not occur, the patient may not be included. However, if the patient's lymphedema has lasted for over 24 months, if she currently is smoking or if there are any untreated or uncontrolled primary breast-cancer, which can cause further damage to the lymphatics and influence the measurements of this study, the patient is excluded from the study, see table 2.

Inclusion criteria:	Exclusion criteria:

 
• Female
 
	
 
• Duration of disease over 24 months
 

 
• Iatrogenic lymphedema following treatment for breast cancer in upper extremity
 
	
 
• Smoker
 

 
• Possible to obtain informed consent
 
	
 
• Untreated or uncontrolled primary cancer
 

 
• Age>18
 
	
 
• No applicable lymphatic vessels identified, using ICG lymphangiography
 

	
 
• No applicable venous vessels identified using ultra high frequency ultrasound
 

*Table 2: Patient inclusion and exclusion criteria.*

Included participants will undergo surgical intervention with LVA, in the affected upper extremity. Prior to surgery, pre-operative mapping of relevant lymph- and venous vessels using respectively ICG lymphography and ultra high frequency ultrasound for visualization, evaluation and selection, will be performed.

During real-time ICG lymphangiography, lymphatic vessels are mapped on the patient's arm, in relation to its dermal backflow pattern. Then, following the mapped lymphatic vessels using ultra high frequency ultrasound, venules will be identified nearby and equally mapped. Videos and pictures of the patient arms and ICG lymphangiography will subsequently be performed.

After detection of applicable vessels per-operatively, the lymphatic vessels and venules will be dissected and anastomosed in a ratio of 1:1.

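### Table 2 makes failed mapping by the imaging under test an exclusion, so the primary comparison is conditional on successful mapping and the protocol provides no denominator of imaged candidates

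*Protocol*

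**What the plan says.** The Introduction and Background give the primary aim: to test whether the two imaging methods together correctly identify lymphatic vessels and nearby venules before LVA. Collection of Data defines the primary outcome as vessels found at surgery against vessels planned.

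Table 2 in Design and population has two exclusion criteria that are results of those methods: "No applicable lymphatic vessels identified, using ICG lymphangiography" and "No applicable venous vessels identified using ultra high frequency ultrasound". The same section invites only patients already judged clinically to be LVA candidates.

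On the order of events:
- After Table 2 the protocol says "Included participants will undergo surgical intervention with LVA, in the affected upper extremity". It then describes "Prior to surgery, pre-operative mapping of relevant lymph- and venous vessels using respectively ICG lymphography and ultra high frequency ultrasound", and the ultrasound step follows the ICG step: "Then, following the mapped lymphatic vessels using ultra high frequency ultrasound, venules will be identified nearby and equally mapped".
- Design and population says "Only patients who provide written, informed consent will be enrolled in the project".
- Database says that consent "is obtained at the patients' first consultation in the outpatient clinic" and adds "No data is collected nor known to the researcher prior to this".

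The planned size is 10 patients, justified by feasibility alone. Material and methods sets a minimum of two anastomosis sites per extremity. Table 2 excludes only when no applicable vessel is found.

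**The concern.** Eligibility depends on the result of the methods being evaluated. A clinically suitable candidate in whom ICG shows no usable lymphatic, or ultrasound no usable vein, leaves the study under Table 2. The patients who remain are selected on imaging success.

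Two questions need to be kept apart. The first is confirmation: when a vessel has been mapped, is it found at surgery? The primary outcome addresses this among operated patients, and it can still come out badly. The second is yield: in what share of imaged candidates does the method give a usable map? The Background hopes for an algorithm to choose between surgery and other treatments, and Sample size and Statistics says positive results will lead to a larger study. Both depend on yield as well as confirmation, and the protocol provides no denominator for yield. A reader could then take high agreement among operated patients as performance in all LVA candidates.

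**Working it through.** **No plan figure to reproduce.** The protocol states no power, accuracy or mapping-failure figure. The main check sets eligibility against aim and outcome.

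**Step 1: what Table 2 fixes.** A patient enters the primary comparison only with at least one applicable lymphatic (ICG) and at least one applicable vein (ultrasound). Patient-level mapping success among the 10 is then 10/10 by construction, whatever the true yield.

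**Step 2: what the text provides for the others.** Database lists the numbers of mapped and applicable vessels, but no count of patients in whom mapping failed. No section says that such patients are reported, replaced or kept in a denominator.

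**Step 3: when the exclusion acts.** Mapping is described for participants already included, and the primary investigator takes part in the ICG step. No data are known to the researcher before consent, and enrolment is tied to consent. This points to an exclusion after consent. Yet a criterion in an eligibility table can equally be read as screening. The document does not settle it.

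**Step 4: illustration.** The number of failed mappings, m, is an assumption. The 10 are taken as operated patients, which is the most natural reading. Yield = 10/(10 + m), with exact (Clopper-Pearson) 95% intervals.

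| m | Imaged | Yield | Exact 95% CI |
|---|---|---|---|
| 1 | 11 | 10/11 = 90.9% | 58.7% to 99.8% |
| 2 | 12 | 10/12 = 83.3% | 51.6% to 97.9% |
| 3 | 13 | 10/13 = 76.9% | 46.2% to 95.0% |

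If imaging continues until 10 patients are mapped, the lower limits are unchanged and the upper limits become 99.7%, 97.7% and 94.5%.

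On the less natural reading, with the 10 counted at consent, the comparison would rest on 9, 8 or 7 patients. Yield would be 90% (55.5% to 99.7%), 80% (44.4% to 97.5%) or 70% (34.8% to 93.3%).

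**Step 5: is a failure likely to occur at all?** With f the assumed share of unmappable candidates, the chance of at least one among 10 imaged is 1 - (1 - f)^10. This is 65% at f = 10%, 89% at 20% and 97% at 30%. If none occurs, reporting 0 of 10 would still be informative: the one-sided 95% upper bound is 1 - 0.05^(1/10) = 25.9%.

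**The case against.** The strongest reply is that conditioning is built into the question. With nothing planned there is nothing to compare, mapping yield is not a stated outcome, and this is a hypothesis-generating pilot of 10 with no power claim. A finding of no applicable vessel may also be a true absence. All of this stands. It means the comparison is not invalid, and that unmapped patients inform yield and not accuracy. It does not remove the point, because the rule itself takes out patients who bear on the protocol's own intended use.

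A second reply is that counts of excluded patients and labelling belong in the analysis plan or the report. That is partly right, and silence alone would be no finding. But eligibility is fixed in this protocol, and an analysis plan cannot readily restore patients whom the protocol excludes.

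Four stronger readings are tempting, and the document does not support them:
- That unmappable patients will certainly go uncounted. The protocol does not say that no screening log is kept.
- That enrolled patients are definitely removed after consent. This is an inference from several sections.
- That the meaning of the 10 is wholly open. Included participants undergo LVA and are followed after it, so operated patients is the natural reading.
- That an assumed 90% confirmation rate would fall to 82%, 75% or 69% when multiplied by the yields above. This uses assumed rates and scores as confirmation failures patients who had nothing to confirm.

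The imaging criteria appear in Table 2 and not in the surrounding prose. That is no contradiction, since the prose refers to the table.

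**Conclusion.** The point holds in a limited form. Table 2 turns the results of the two methods under test into study exclusions. The planned-versus-found comparison remains valid, but only for patients with at least one applicable lymphatic and one applicable vein mapped. The protocol provides no denominator of imaged LVA candidates.

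No protocol figure changes. The size is unknown because no failure rate is given; the yields shown rest on assumed counts of 1 to 3 failed mappings. The intervals are wide, so a pilot of this size can give only a rough yield. The change is worth making because it affects what the result can be used for and costs little.

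Two further matters need reconciling: the order of inclusion and mapping, and the two-site minimum against the Table 2 threshold, which leaves a patient with a single mapped pair unclear.

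**What to change.** Without changing who is operated on:

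1. Define the imaged set as all consented LVA candidates who undergo ICG and ultrasound mapping.
2. In Table 2, move the two imaging criteria out of the study exclusions. Record a finding of no applicable vessel as a mapping result, noting whether mapping stopped at the ICG or the ultrasound step.
3. Reword the Design and population sentence that sends included participants to LVA so that it refers to the mapped, operated subset. Without this, removing the criteria would make the text imply surgery for unmapped patients.
4. State that the planned 10 are operated patients.
5. Report the number imaged and the number and proportion with an applicable lymphatic-venule pair, with an exact interval. For those not mapped, give the baseline data already listed in Database, such as duration, stage and BMI.
6. Present the primary comparison as conditional on successful mapping.
7. Reconcile the order of inclusion and mapping across Design and population, Collection of Data and Database. Reconcile the two-site minimum in Material and methods with the Table 2 threshold, and use the reconciled threshold in the yield definition.

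The cost is wording in those sections and slightly more record keeping, largely from data already planned. The downside is a yield that may look less favourable and will be imprecise.
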